9.1.2 Discontinuation from study

Discontinuation from study is when the subject permanently stops receiving the study treatment, and further protocol-required assessments or follow-up, for any reason.

If the subject agrees, a final evaluation at the time of the subject's study discontinuation should be made as detailed in the assessment table (refer to Section 8).

9.1.3 Lost to follow-up

For subjects whose status is unclear because they fail to appear for study visits without stating an intention to discontinue or withdraw, the investigator must show "due diligence" by documenting in the source documents steps taken to contact the subject, e.g. dates of telephone calls, registered letters, etc. A subject should not be considered as lost to follow-up until due diligence has been completed or until the end of the study.

9.2 Withdrawal of informed consent/Opposition to use data/biological samples

Withdrawal of consent/opposition to use data/biological samples occurs when a subject:

• Explicitly requests to stop use of their biological samples and/or data (opposition to use subject's data and biological samples)

and

• No longer wishes to receive study treatment

and

• Does not want any further visits or assessments (including further study-related contacts)

This request should be in writing (depending on local regulations) and recorded in the source documentation.

In this situation, the investigator should make a reasonable effort (e.g. telephone, e-mail, letter) to understand the primary reason for the subject's decision to withdraw their consent/opposition to use data/biological samples and record this information.

Where consent to the use of Personal and Coded Data is not required in a certain country's legal framework, the subject therefore cannot withdraw consent. However, they still retain the right to object to the further collection or use of their Personal Data.

Study treatment must be discontinued and no further assessments conducted, and the data that would have been collected at subsequent visits will be considered missing.

Further attempts to contact the subject are not allowed unless safety findings require communicating or follow-up.

Clinical Trial Protocol (Version No. 03)

Protocol No. CSAF312B12201

If the subject agrees, a final evaluation at the time of the subject's withdrawal of consent/opposition to use data/biological samples should be made as detailed in the assessment table (refer to Section 8).

Novartis will continue to retain and use all research results (data) that have already been collected for the study evaluation, including processing of biological samples that has already started at time of consent withdrawal/opposition. No new Personal Data (including biological samples) will be collected following withdrawal of consent/opposition.

9.3 Study completion and post-study treatment

Study completion is defined as when the last subject finishes their Study Completion visit and any repeat assessments associated with this visit have been documented and followed-up appropriately by the Investigator or, in the event of an early study termination decision, the date of that decision.

Sites will contact the subjects by telephone 4 days after EOT visit (Visit 6) to inquire about any adverse events that began after the last treatment with IMP. The investigator must show "due diligence" by documenting in the source documents steps taken to contact the subject, e.g. dates of telephone calls.

9.4 Early study termination by the sponsor

The study can be terminated by Novartis at any time.

Reasons for early termination:

- Unexpected, significant, or unacceptable safety risk to subjects enrolled in the study
- Decision based on recommendations from applicable board(s) after review of safety and efficacy data
- Discontinuation of study drug development

In taking the decision to terminate, Novartis will always consider subject welfare and safety. Should early termination be necessary, subjects must be seen as soon as possible and treated as a subject who discontinued from study treatment: The investigator should contact such information to the subject, when the subject should stop taking drug, when the subject should come in for a final visit(s) that the safety follow up period must be completed if applicable and which visits to be performed. The investigator may be informed of additional procedures to be followed in order to ensure that adequate consideration is given to the protection of the subject's interests. The investigator or sponsor depending on local regulation will be responsible for informing IRBs/IECs of the early termination of the trial.

10 Safety monitoring and reporting

10.1 Definition of adverse events and reporting requirements

10.1.1 Adverse events

An AE is any untoward medical occurrence (e.g. any unfavorable and unintended sign [including abnormal laboratory findings], symptom or disease) in a subject or clinical investigation subject after providing written informed consent for participation in the study. Therefore, an AE may or may not be temporally or causally associated with the use of a medicinal (investigational) product.

The investigator has the responsibility for managing the safety of individual subject and identifying adverse events.

Novartis qualified medical personnel will be readily available to advise on trial related medical questions or problems.

The occurrence of adverse events must be sought by non-directive questioning of the subject at each visit during the study. Adverse events also may be detected when they are volunteered by the subject during or between visits or through physical examination findings, laboratory test findings, or other assessments.

Adverse events must be recorded under the signs, symptoms, or diagnosis associated with them, accompanied by the following information (as far as possible) (if the event is serious refer to Section 10.1.2):

1. The severity grade

mild: usually transient in nature and generally not interfering with normal activities moderate: sufficiently discomforting to interfere with normal activities

severe: prevents normal activities

- 2. Its relationship to the study treatment. If the event is due to lack of efficacy or progression of underlying illness (i.e. progression of the study indication) the assessment of causality will usually be 'Not suspected.' The rationale for this guidance is that the symptoms of a lack of efficacy or progression of underlying illness are not caused by the trial drug, they happen in spite of its administration and/or both lack of efficacy and progression of underlying disease can only be evaluated meaningfully by an analysis of cohorts, not on a single subject
- 3. Its duration (start and end dates or ongoing) and the outcome must be reported
- 4. Whether it constitutes a SAE (see Section 10.1.2 for definition of SAE) and which seriousness criteria have been met
- 5. Action taken with study treatment

All adverse events must be treated appropriately. Treatment may include one or more of the following:

- Dose not changed
- Dose Reduced/increased

- Drug interrupted/permanently discontinued
- 6. its outcome

Conditions that were already present at the time of informed consent should be recorded in medical history of the subject.

Adverse events (including lab abnormalities that constitute AEs) should be described using a diagnosis whenever possible, rather than individual underlying signs and symptoms.

Adverse event monitoring should be continued until the end of study visit.

Once an AE is detected, it should be followed until its resolution or until it is judged to be permanent (e.g. continuing at the end of the study), and assessment must be made at each visit (or more frequently, if necessary) of any changes in severity, the suspected relationship to the interventions required to treat it, and the outcome.

Information about adverse drug reactions for the investigational drug can be found in the Investigator's Brochure (IB).

10.1.2 Serious adverse events

An SAE is defined as any AE [appearance of (or worsening of any pre-existing)] undesirable sign(s), symptom(s), or medical conditions(s) which meets any one of the following criteria:

- fatal
- life-threatening

Life-threatening in the context of a SAE refers to a reaction in which the subject was at risk of death at the time of the reaction; it does not refer to a reaction that hypothetically might have caused death if it were more severe (please refer to the ICH-E2D Guidelines).

- results in persistent or significant disability/incapacity
- constitutes a congenital anomaly/birth defect
- requires inpatient hospitalization or prolongation of existing hospitalization, unless hospitalization is for:
 - routine treatment or monitoring of the studied indication, not associated with any deterioration in condition
 - elective or pre-planned treatment for a pre-existing condition that is unrelated to the indication under study and has not worsened since signing the informed consent
 - social reasons and respite care in the absence of any deterioration in the subject's general condition
 - treatment on an emergency outpatient basis for an event not fulfilling any of the definitions of a SAE given above and not resulting in hospital admission
- is medically significant, e.g. defined as an event that jeopardizes the subject or may require medical or surgical intervention to prevent one of the outcomes listed above

Medical and scientific judgment should be exercised in deciding whether other situations should be considered serious reactions, such as important medical events that might not be immediately life threatening or result in death or hospitalization but might jeopardize the subject or might require intervention to prevent one of the other outcomes listed above. Such events should be considered as "medically significant." Examples of such events are intensive treatment in an emergency room or at home for allergic bronchospasm, blood dyscrasias, or convulsions that do not result in hospitalization or development of dependency or abuse (please refer to the ICH-E2D Guidelines).

All malignant neoplasms will be assessed as serious under "medically significant" if other seriousness criteria are not met.

Any suspected transmission via a medicinal product of an infectious agent is also considered a serious adverse reaction.

10.1.3 SAE reporting

To ensure subject safety, every SAE, regardless of causality, occurring after the subject has provided informed consent and until 30 days after the last study visit must be reported to Novartis safety immediately, without undue delay, under no circumstances later than within 24 hours of learning of its occurrence. Detailed instructions regarding the submission process and requirements are to be found in the investigator folder provided to each site. Information about all SAEs is collected and recorded on the eSAE with paper back. Serious Adverse Event Report Form; all applicable sections of the form must be completed in order to provide a clinically thorough report.

All follow-up information for the SAE including information on complications, progression of the initial SAE and recurrent episodes must be reported as follow-up to the original episode within 24 hours of the investigator receiving the follow-up information. An SAE occurring at a different time interval or otherwise considered completely unrelated to a previously reported one must be reported separately as a new event.

If the SAE is not previously documented in the Investigator's Brochure or Package Insert (new occurrence) and is thought to be related to the study treatment, a CMO & PS Department associate may urgently require further information from the investigator for health authority reporting. Novartis may need to issue an Investigator Notification to inform all investigators involved in any study with the same study treatment that this SAE has been reported.

Suspected Unexpected Serious Adverse Reactions (SUSARs) will be collected and reported to the competent authorities and relevant ethics committees in accordance with European Union (EU) Guidance 2011/C 172/01 or as per national regulatory requirements in participating countries.

Any SAEs experienced after the 30 day period after the last study visit should only be reported to Novartis Safety if the investigator suspects a causal relationship to study treatment.

10.1.4 Pregnancy reporting

Pregnancies

If a female trial subject becomes pregnant, the study treatment should be stopped, and the pregnancy consent form should be presented to the trial subject. The subject must be given adequate time to read, review and sign the pregnancy consent form. This consent form is

necessary to allow the investigator to collect and report information regarding the pregnancy. To ensure subject safety, each pregnancy occurring after signing the informed consent must be reported to Novartis within 24 hours of learning of its occurrence. The pregnancy should be followed up to determine outcome, including spontaneous or voluntary termination, details of the birth, and the presence or absence of any birth defects, congenital abnormalities, or maternal and/or newborn complications.

Pregnancy should be recorded and reported by the investigator to the Novartis Chief Medical Office and Patient Safety (CMO&PS). Pregnancy follow-up should be recorded on the same form and should include an assessment of the possible relationship between the use of SAF312 eye drops and any pregnancy outcome. Any SAE experienced during pregnancy must be reported.

If a female partner of a male trial subject who took study treatment in this study becomes pregnant, pregnancy outcomes should be collected. Consent to report information regarding these pregnancy outcomes should be obtained from the mother.

After consent is provided, the pregnancy reporting will occur up to one year after the estimated date of delivery.

10.1.5 Reporting of study treatment errors including misuse/abuse

Medication errors are unintentional errors in the prescribing, dispensing, administration or monitoring of a medicine while under the control of a healthcare professional, subject or consumer (European Medicines Agency (EMA) definition).

Misuse refers to situations where the medicinal product is intentionally and inappropriately used not in accordance with the protocol.

Abuse corresponds to the persistent or sporadic, intentional excessive use of a medicinal product, which is accompanied by harmful physical or psychological effects.

Study treatment errors and uses outside of what is foreseen in the protocol will be recorded on the appropriate CRF irrespective of whether or not associated with an AE/SAE and reported to Safety only if associated with an SAE (see Table 10-1). Misuse or abuse will be collected and reported in the safety database within 24 hours of Investigator's awareness only if it is associated with an SAE.

Table 10-1 Guidance for capturing the study treatment errors including misuse/abuse

Treatment error type	Document as a protocol deviation (Yes/No)	Document in AE eCRF	Complete SAE form
Unintentional study treatment error	Yes	Only if associated with an AE	Only if associated with an SAE
Misuse/Abuse	Yes	Only if associated with an AE	Only if associated with an SAE

For more information on AE and SAE definition and reporting requirements, please see the respective sections.

10.2 Additional Safety Monitoring

Not applicable

11 Data Collection and Database management

11.1 Data collection

Designated investigator staff will enter the data required by the protocol into the Electronic CRF (eCRF). The eCRFs have been built using fully validated secure web-enabled software that conforms to 21 Code of Federal Regulation (CFR) Part 11 requirements, Investigator site staff will not be given access to the EDC system until they have been trained. Automatic validation programs check for data discrepancies in the eCRFs, allow modification and/or verification of the entered data by the investigator staff.

The investigator/designee is responsible for assuring that the data (recorded on CRFs) (entered into eCRF) is complete, accurate, and that entry and updates are performed in a timely manner. The Investigator must certify that the data entered are complete and accurate

After final database lock, the investigator will receive copies of the subject data for archiving at the investigational site.

All data should be recorded, handled, and stored in a way that allows its accurate reporting, interpretation, and verification.

11.2 Database management and quality control

Novartis personnel will review the data entered by investigational staff for completeness and accuracy. Electronic data queries stating the nature of the problem and requesting clarification will be created for discrepancies and missing values and sent to the investigational site via the EDC system. Designated investigator site staff are required to respond promptly to queries and to make any necessary changes to the data.

Concomitant treatments and prior medications entered into the database will be coded using the World Health Organization (WHO) Drug Reference List, which employs the Anatomical Therapeutic Chemical classification system. Medical history/current medical conditions and adverse events will be coded using the Medical Dictionary for Regulatory Activities (MedDRA) terminology.

Randomization codes and data about all study treatment (s) dispensed to the subject and all dosage changes will be tracked using an Interactive Response Technology (IRT). The system will be supplied by a vendor, who will also manage the database. The data will be sent electronically to Novartis at specific timelines.

Each occurrence of a code break via IRT will be reported to the clinical team and study monitor. The code break functionality will remain available until study shut down or upon request of Novartis.

Once all the necessary actions have been completed and the database has been declared to be complete and accurate, it will be locked **and the treatment codes will be unblinded** and made

Protocol No. CSAF312B12201

available for data analysis. Any changes to the database after that time can only be made after written agreement by Novartis development management.

11.3 Site monitoring

Before study initiation, at a site initiation visit or at an investigator's meeting, a Novartis representative will review the protocol and data capture requirements (i.e. eCRFs) with the investigators and their staff. During the study, Novartis employs several methods of ensuring protocol and GCP compliance and the quality/integrity of the sites' data. The study monitor will visit the site to check the completeness of subject records, the accuracy of data capture / data entry, the adherence to the protocol and to Good Clinical Practice (GCP), the progress of enrollment, and to ensure that study treatment is being stored, dispensed, and accounted for according to specifications. Key study personnel must be available to assist the study monitor during these visits. Continuous remote monitoring of each site's data may be performed by a centralized Novartis/Clinical Research Associate (CRA) organization. Additionally, a central analytics organization may analyze data & identify risks & trends for site operational parameters, and provide reports to Novartis clinical teams to assist with trial oversight.

The investigator must maintain source documents for each subject in the study, consisting of case and visit notes (hospital or clinic medical records) containing demographic and medical information, laboratory data, electrocardiograms, and the results of any other tests or assessments. All information on CRFs must be traceable to these source documents in the subject's file. The investigator must also keep the original informed consent form signed by the subject (a signed copy is given to the subject).

The investigator must give the study monitor access to all relevant source documents to confirm their consistency with the data capture and/or data entry. Novartis monitoring standards require full verification for the presence of informed consent, adherence to the inclusion/exclusion criteria, documentation of SAEs, and of data that will be used for all primary variables. Additional checks of the consistency of the source data with the CRFs are performed according to the study-specific monitoring plan. No information in source documents about the identity of the subjects will be disclosed.

12 Data analysis and statistical methods

Any data analysis carried out independently by the investigator should be submitted to Novartis before publication or presentation.

12.1 Analysis sets

The Full Analysis Set (FAS) comprises all subjects to whom study treatment has been assigned by randomization. According to the intent to treat principle, subjects will be analyzed according to the treatment and strata they have been assigned to during the randomization procedure.

The Safety Set includes all subjects who received at least one dose of study treatment. Subjects will be analyzed according to the study treatment received, where treatment received is defined as the randomized treatment if the subject took at least one dose of that treatment or the first treatment received if the randomized treatment was never received.

Page 57

Protocol No. CSAF312B12201

12.2 Subject demographics and other baseline characteristics

Demographic and other baseline data including disease characteristics will be listed and summarized descriptively by treatment group for the FAS.

Categorical data will be presented as frequencies and percentages. For continuous data, mean, standard deviation (SD), median, minimum, and maximum will be presented. For selected parameters, 25th and 75th percentiles will also be presented.

Relevant medical histories and current medical conditions at baseline will be summarized by system organ class and preferred term, by treatment group.

12.3 Treatments

The Safety set will be used for the analyses below. Categorical data will be summarized as frequencies and percentages. For continuous data, mean, SD, median, 25th and 75th percentiles, minimum, and maximum will be presented.

The duration of exposure in days to SAF312 and placebo will be summarized by means of descriptive statistics using the safety set.

Concomitant medications and significant non-drug therapies prior to and after the start of the study treatment will be listed and summarized according to the Anatomical Therapeutic Chemical (ATC) classification system, by treatment group.

12.4 Analysis of supporting primary objectives

The analysis of the primary endpoints will be based on FAS.

12.4.1 Definition of primary endpoint(s)

The primary endpoint is the change from baseline in weekly mean pain severity VAS at Week 12. The weekly mean pain severity VAS will be calculated as the mean of the daily pain severity VAS from the 7 days of the week. Baseline value will be calculated as the mean of the daily pain severity VAS from the 7 days prior to the first dose.

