4.1 Rationale for study design

This study will evaluate the safety and efficacy of two concentrations of SAF312 twice daily for 12 weeks in the treatment of CICP following refractive or cataract surgery. The aim is to evaluate the treatment effect of SAF312 compared to placebo, and to determine the appropriate concentration to carry forward for further development.

The active and placebo IMPs will be presented in identical packaging to ensure no bias to the study results due to knowledge of the treatment assignment. Due to the difference in appearance of SAF312 eye drops vs placebo eye drops (milky white vs clear, respectively), sites will be required to have an unblinded staff member to manage drug dispensation, drug accountability, as well as collection of adverse events or subject reports of product comments/complaints. All other site staff and Sponsor staff will be blinded to treatment assignments. To ensure masking of subjects to their treatment assignment, no subject will receive both placebo and active treatment so no change in appearance of the test article will be noticeable by a particular subject. Subjects may be informed that their study treatment may appear cloudy or white, but must not be informed about the specific identity of the treatments based on differences in appearance.

A 12-week observation period prior to randomization is included as a method to confirm the chronicity of their ocular pain, observe trends in the subject's pain occurrences (
), and to observe behaviors with artificial tears and rescue medications prior to receiving randomized treatment. This observation period confirms the selection of

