5.1 Inclusion criteria

Subjects eligible for inclusion in this study must meet all of the following criteria:

- 1. Subjects \geq 18 years old who have given written informed consent.
- 2a. Subjects who have undergone refractive surgery (PRK, LASIK, LASEK, RK, or SMILE) or cataract surgery in both eyes, with or without refractive enhancement in one or both eyes, >4 months prior to Screening Visit and experiencing persistent ocular surface pain since the surgery, and have been seen by an ophthalmologist or optometrist at least once with complaint of continued ocular pain since surgery.
 - **NOTE:** The 4 month requirement must be based on the date of the last surgery.
- 3a. Subjects with worst ocular pain severity (VAS) of \geq 30 mm) over the last 7 days prior to screening.
- 4. Subjects who demonstrate $a \ge 60\%$ reduction in ocular pain within 5 minutes after instillation of a single topical ocular anesthetic drop at Screening Visit (as calculated by the electronic Patient Reported Outcome (ePRO) device).

At Baseline Visit

- 5a. Subjects with an average pain severity VAS score of \geq 30 mm based on Daily eDiary for the last 7 days prior to Baseline Visit (Visit 2).
- 6. Subject who have reported pain severity VAS score > 10 mm based on Daily eDiary for > 50% of the days of the 12-week observational period (as calculated in the ePRO portal).

5.2 **Exclusion criteria**

Subjects meeting **any** of the following criteria are not eligible for inclusion in this study.

- 1a. Use of corrective contact lenses within 14 days of the Screening Visit and any use of corrective contact lenses for the duration of the study (bandage or scleral lenses are permitted).
- 2. Use of artificial tears, gels, lubricants or pain medication within 4 hours of conducting assessments at the Screening Visit.
- 3. Use of nerve growth factor eye drops within 14 days of the Screening Visit.
- 4. Seasonal allergic conjunctivitis, or other acute or seasonal ocular diagnosis that are active at the time of Screening or Baseline visits or would be active during the course of the
- 5. Any history of ocular herpes simplex virus or herpes zoster virus infection, or other severe ocular conditions such as graft versus host disease, Stevens-Johnson syndrome, sarcoidosis.
- 6. Presence of any ocular infection (bacterial, viral, or fungal) within 30 days prior to Screening Visit.

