12.8 Sample size calculation

12.8.1 Primary endpoint(s)

Assuming a true treatment difference in change from baseline in weekly mean pain severity VAS of 15 mm and a SD of 23 mm, a sample size of 50 subjects per arm provides approximately 83% power that the primary analysis will be statistically significant at the two-sided 5% significance level adjusted by 2 comparisons.

See Table 12-1 for power to detect a significant difference from placebo under various assumed treatment effect of weekly mean pain severity VAS and SD.

nQuery Advisor 7.0 is used for the estimate.

Table 12-1 Power to detect a significant difference from placebo under different assumed treatment effects and SD with N = 50 pts/arm

	Treatment effect: difference from placebo in change from baseline in weekly mean pain severity VAS			
SD of change from baseline in weekly mean I pain severity VAS	15	20		
17	98%	>99%		
20	92%	>99%		
23	83%	97%		

The sample size may increase by up to 20% (i.e., 60 pts/arm) in order to maintain power in case dropout increases during the pandemic.

13 Ethical considerations and administrative procedures

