2.1.1.5 Visit Windows

Visit windows will be applied for all measurements except data from e-diary daily. Weekly mean will be calculated every 7 days starting from study day 1.

Novartis	For business use only	Page 11 of 33
SAP		CSAF312B12201

Allocation of accomments to enclusio visit window

Table 2-1 Allocation of assessments to analysis visit window				
Scheduled main visit name/label	Target study day	Analysis visit window in study days	Visit Label	
Visit 1 Screening	-84	≤ -1	Screening	
Visit 2 Baseline	1	1	Baseline	
Visit 3	14	2 - 21	Visit 3 (week 2)	
Visit 4	28	22 - 42	Visit 4 (week 4)	
Visit 5	56	43 - 70	Visit 5 (week 8)	
Visit 6 EOT	84	≥ 71	Visit 6 / EOT (week 12)	

To allocate assessments to each scheduled visit

Table 04

- If no measurement is available within a visit window, the assessment will be considered missing for the visit.
- If there is more than one measurement available within the same visit window, use the following rules:
 - 1. The record closest to the target day will be used.
 - 2. If there are multiple records with the same distance to the target day, the latest record will be used.
 - 3. If there are multiple records with the same distance on the same day, the average will be used.

2.1.1.6 7-day average of assessments

The Pain Severity Visual Analog Scale (VAS) score is captured in the e-diary daily by the patient for the entire 6 months of the study (observational period and treatment period), and weekly mean of the scores is calculated by averaging the available Pain Severity VAS scores during the 7 days of that week. Pain frequency will be analyzed in the same manner.

To calculate the frequency of artificial tear/gel/lubricant use, the information is captured daily as mentioned above, and the daily frequency collected by the patient in e-diary during the 7 days of that week will be averaged.

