5.2 Statistical models

5.2.1 Primary Analysis

The following MMRM model will be used for the primary estimand and supplementary estimand:

change from baseline in weekly mean pain severity VAS score = intercept + baseline weekly mean pain severity VAS score + treatment + week + treatment*week + baseline weekly mean pain severity VAS score * week + error

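### The primary model adjusts only for the last 7 of 84 run-in diary days; adding the mean of the earlier 11 weeks as a second covariate would probably improve precision, by an amount that the documents do not fix

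*Protocol*

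**What the plan says.** The severity VAS is captured daily "for the entire 6 months of the study (observational period and treatment period") according to SAP 2.1.1.6. The run-in has a stated purpose in Protocol 4.1: "A 12-week observation period prior to randomization is included as a method to confirm the chronicity of their ocular pain". That section also mentions observing trends in pain and the use of tears and rescue medication.

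For the primary endpoint, Protocol 12.4.1 defines baseline narrowly: "Baseline value will be calculated as the mean of the daily pain severity VAS from the 7 days prior to the first dose". The model in SAP 5.2.1 begins "intercept + baseline weekly mean pain severity VAS score + treatment + week + treatment*week" and adds only the baseline-by-week interaction. Protocol 12.4.2 and SAP 2.5.2 describe the same terms.

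The final 7 days have two other uses. Inclusion 5a requires a mean of at least 30 mm "based on Daily eDiary for the last 7 days prior to Baseline Visit (Visit 2"), and Protocol 6.3.2 stratifies randomisation on the 7-day mean, cut at 75 mm. The full 12 weeks are used for inclusion 6 (above 10 mm on more than half of the days). No efficacy model in either document uses the first 11 weeks.

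**The concern.** Two subjects with the same final-week mean can have had quite different pain over the preceding 11 weeks. If each subject has a fairly stable level with week-to-week fluctuation around it, one week is a noisy reading of that level. Requiring that week to be at least 30 mm also restricts its range, which weakens it further as a predictor. The earlier weeks would then carry information about Week 12 pain that the final week lacks, and the variance they could explain stays in the error term.

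What is at stake is precision, with about 50 subjects per arm and two comparisons against placebo. The data are already collected, so any gain needs no extra enrolment. The plan, by contrast, allows up to 60 per arm to protect power against dropout (Protocol 12.8.1). A covariate that predicts Week 12 pain may also make the missing-at-random assumption more plausible for subjects with few on-treatment weeks. I have not tried to quantify that.

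**Working it through.** **1. The plan's own power figure.** Inputs from Protocol 12.8.1: a difference of 15 mm, an SD of 23 mm for the change score, and the claim that "a sample size of 50 subjects per arm provides approximately 83% power". The test level is given as "the two-sided 5% significance level adjusted by 2 comparisons", which I read as 0.05/2 = 0.025 per comparison.

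- Noncentrality = 15 / (23 × √(2/50)) = 15 / 4.6 = 3.26, with 98 df.
- Two-sample t-test power at two-sided 0.025 is 83.6%, so the stated 83% reproduces. The other cells of Table 12-1 agree within 2 points.
- With the Dunnett critical value (2.235, 147 df), power is 84.6%.

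This calculation uses the SD of change and takes no credit for any covariate.

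**2. What a second covariate can add, before selection.** Scale the weekly mean to variance 1. Let r be the correlation between the last run-in week and Week 12, which are 12 weeks apart. The residual variance given the last week is V7 = 1 − r². The last week plus the 12-week mean carries the same information as the last week plus the mean of the earlier 11 weeks, so either pair gives the residual variance of the proposed model, V2.

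- *Stable share s, independent weekly noise.* Here r = s and V2 = 1 − s² / (s + (1−s)/12). For s = 0.5: V2 = 1 − 0.25/0.5417 = 0.538, V7 = 0.75, ratio 0.72. For s = 0.4 the ratio is 0.77; for s = 0.8 it is 0.60.
- *Stable level plus moderate drift.* Shares of 0.6 stable, 0.3 drift (week-to-week correlation 0.8) and 0.1 noise give 0.82. Shares of 0.5, 0.4 (correlation 0.9) and 0.1 give 0.92.
- *Little or no stable level, slow drift.* Ratios are 0.96 to 1.00. With pure first-order drift the last week already holds all the usable information, so the gain is zero.

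**3. With the entry rules applied.** Assumptions, none from the documents: population mean 50 mm, weekly SD 22 mm, correlation between weeks = share + (1 − share) × ρ^lag, values clipped to 0-100, 200,000 subjects per scenario. Subjects were kept if the baseline week was at least 30 mm and more than half of the weekly means exceeded 10 mm. Some scenarios add on-treatment variability. The rows below have an SD of change near 23 mm.

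| Stable share | ρ | Added on-treatment SD (mm) | SD of change (mm) | Cut in Week 12 residual variance |
|---|---|---|---|---|
| 0 | 0.9 | 0 | about 24 | 0% |
| 0.1 | 0.9 | 0 | about 23 | under 1% |
| 0.5 | 0.9 | 15 | about 22.5 | 2% |
| 0.2 | 0.8 | 0 | about 24 | 3% |
| 0.3 | 0.8 | 0 | about 23 | 5% |
| 0.3 | 0.7 | 0 | about 23.5 | 8% |
| 0.3 | 0.3 | 0 | about 24 | 15% |
| 0.5 | 0.3 | 12 | about 23 | 18% |

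Away from 23 mm, the most favourable case (share 0.7, ρ 0.3) gives about 33%. At ρ = 0.9 with a share up to 0.5, the earlier 11-week mean used alone predicts slightly worse than the last week.

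**4. Translation to power.** Take 23 mm as the residual SD with the 7-day covariate in place. For variance ratio R, the new SD is 23√R, the equivalent sample size is 50R per arm, and the confidence interval narrows by 1 − √R.

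| R | SD (mm) | Power | Same precision as now with, per arm |
|---|---|---|---|
| 1.00 | 23.0 | 83.6% | 50 |
| 0.96 | 22.5 | 85.2% | 48 |
| 0.91 | 21.9 | 87.1% | 45.5 |
| 0.82 | 20.8 | 90.5% | 41 |
| 0.71 | 19.4 | 94.3% | 35.5 |

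If 23 mm is instead the raw SD of change, the 7-day covariate already helps and the added gain in power is smaller. In the 0.6/0.3/0.1 case of step 2, power goes from 90.9% to 95.5%.

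**The case against.** The strongest reply is that nothing here is an error. A 7-day baseline with a baseline-by-week term is a standard analysis, valid under randomisation, and the 83% power does not rest on the run-in. That stands: this is a possible gain in efficiency.

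Several stronger readings are tempting, and the documents do not support them.

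- *The run-in mean is the better predictor, so precision is certainly lost.* This needs a within-subject correlation that neither document gives. Under slow drift the earlier mean alone is the worse predictor, and adding it gains almost nothing.
- *Matching the planned 23 mm pins the gain at roughly 8-17%.* It does not. That range comes from limiting ρ to 0.3-0.7. Slow-drift structures match 23 mm equally well with gains of 0-5%.
- *Selecting on the baseline week biases the comparison through regression to the mean.* The baseline-by-week term already adjusts for it given baseline, and what remains is shared by all arms.
- *The run-in goes unused.* Inclusion 6 uses all 12 weeks, and Protocol 4.1 gives it descriptive purposes.
- *A subject with 41 days at 0 mm, 36 at 11 mm and 7 at 30 mm is treated as if at 30 mm throughout.* The arithmetic is right: 43/84 = 51% of days above 10 mm, and a mean of (396 + 210)/84 = 7.2 mm, which passes 5a and 6. But 2a (persistent pain since surgery) and 3a (worst pain of at least 30 mm in the week before screening) make such a subject unlikely.
- *Inclusion 6 guarantees that the covariate exists.* It does not for every analysed subject. SAP Table 5-1 keeps in all analysis sets subjects who breach criteria such as 5a and those with diary compliance below 50%.

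**Conclusion.** The point holds as a low-cost improvement to a valid, unbiased analysis. The first 11 weeks of run-in scores enter no stated efficacy model, and using them would probably sharpen the primary comparison. The supported size is a cut in Week 12 residual variance of about 0% to about 30%, and about 0-18% where the SD of change is near 23 mm. With 23 mm as the current residual SD, the latter range corresponds to power between 83.6% and about 90%.

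These figures rest on assumed variance shares and week-to-week correlations. They apply inclusion 6 to weekly means instead of days, leave out 2a and 3a, and do not model missing diary days or the exclusion of rescue-medication days.

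**What to change.** In Protocol 12.4.2 and SAP 2.5.2 and 5.2.1, before unblinding:

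- Keep the 7-day baseline for the change score and as a covariate with its week interaction.
- Add one covariate: the mean daily pain severity VAS over Days -84 to -8 (77 days, 11 weeks), from available entries, with its interaction with week. It must be an addition, because alone it can predict worse than the 7-day mean.
- State a rule for the rare FAS subject with no entry in that period, for example the pooled mean of the covariate, computed blind to treatment.
- Since SAP 2.5.4 reuses the primary model by subgroup, allow the term to be dropped where a small subgroup model does not converge.

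The endpoint, estimand and data collection do not change. The cost is 12 fixed-effect parameters (one main effect and 11 interaction terms, about one degree of freedom per week), one derived variable, and a small text change to both documents. The Protocol part needs a written amendment under Protocol 14.1. Blinded pooled run-in and on-treatment data can show the likely gain before the team commits to the term.
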